9.2.1.3.3 Unsolicited Adverse Events

In addition to recording solicited reactions, subjects or subjects' parents/legally acceptable representatives will be instructed to record any other medical events that may occur between each vaccination and during the 28-day period after the last vaccination and the booster vaccination. Space will be provided in the DC for this purpose.

Information on SAEs will be collected and assessed throughout the study, from inclusion until 6 months after the last vaccination. Any SAE occurring at any time during the study will be reported by the Investigator in the CRB according to the completion instructions provided by the Sponsor; this includes checking the “Serious” box on the AE CRF and completing the appropriate Safety Complementary Information CRFs. All information concerning the SAE is to be reported either as part of the initial reporting or during follow-up reporting if relevant information became available later (eg, outcome, medical history, results of investigations, copy of hospitalization reports). In case a subject experiences febrile convulsion (neurological event associating fever and seizure), the assessment will be performed according to the “Guideline for definition and collection of cases of febrile convolution”, and this event will be considered an SAE.

See [Section 10](#) for further details on SAE reporting.

For each unsolicited AE (whether serious or non-serious), the following information is to be recorded:

- Start and stop dates^a
- Intensity of the event:

For measurable unsolicited AEs that are part of the list of solicited reactions, the size of the AE as well as the temperature for fever will be collected and analyzed based on the corresponding scale used for solicited reactions (see [Table 9.1](#) to [Table 9.5](#)).

All other unsolicited AEs will be classified according to the following intensity scale:

^a The stop date of all related AEs will be actively solicited. For other events, the Investigator will provide the stop date when it becomes available. AEs for which no stop date was obtained during the course of the study will be considered as ongoing at the end of the study.

- Grade 1: A type of AEs that is usually transient and may require only minimal treatment or therapeutic intervention. The event does not generally interfere with usual activities of daily living.
- Grade 2: A type of AEs that is usually alleviated with additional therapeutic intervention. The event interferes with usual activities of daily living, causing discomfort but poses no significant or permanent risk of harm to the research subject.
- Grade 3: A type of AEs that interrupts usual activities of daily living, or significantly affects clinical status, or may require intensive therapeutic intervention.
- Whether the AE was related to the investigational product (for unsolicited systemic AEs)

The Investigator will assess the causal relationship between the AE and the investigational product as either “Not related” or “Related”, as described in [Section 9.2.1.3.5](#).

- Action taken for each AE (eg, medication)

The action(s) taken by the subject or subject’s parent/LAR to treat and/or manage any unsolicited AEs will be classified in the CRB using the following list (all applicable items should be checked):

- None
- Medication
- Health care provider contact
- Hospitalized
- Discontinuation of study vaccination
- Whether the AE was serious
- Whether the AE caused study discontinuation

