9.2.1.2 Safety Endpoints

The secondary endpoints for the evaluation of safety are:

- Occurrence of any unsolicited systemic AEs reported in the 30 minutes after each vaccine injection
- Occurrence of solicited (pre-listed in the subject's DC and electronic CRF) injection site and systemic reactions occurring within 7 days after each injection
- Occurrence of unsolicited (spontaneously reported) injection site reactions occurring within 28 days after each injection and unsolicited systemic AEs up to 28 days after each injection
- Occurrence of SAEs and AESIs within at least 6 months after each vaccination as applicable to Cohort 1 and Cohort 2.
- SAEs (including AESIs) reported throughout the study, including occurrence, nature (Medical Dictionary for Regulatory Activities [MedDRA] preferred term), time of onset, duration, intensity, action taken, relationship to the product administered (for systemic AEs only),

whether the event caused termination from the study, outcome, elapsed time from last administration (if less than 24h), relationship to study procedures, and seriousness criterion

Note: The following AESIs will be considered as SAEs and reported to the Sponsor: anaphylactic reactions, encephalitis, and convulsions. For each AESI, the standard case definitions from the Brighton Collaboration will be used. These AESIs have been defined based on existing post-marketing safety data of other rabies vaccines.

Note: Information about SAEs, AESIs, and cases of pregnancy were recorded throughout the study for pediatrics and adults in Cohort 1; and this is up to 6 months after the booster dose for subset of adults in Cohort 1. Information about SAEs, AESIs, and cases of pregnancy will be recorded until 6 months after the primary series (V05) and until 6 months after the booster dose for subset of adults in Cohort 2. Between the 6-month follow-up visit after primary series (V05) and booster dose visit (V08), AESIs will not be collected, only fatal SAEs and related SAEs will be collected.

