#### 4.3.1.2 Unsolicited AEs (Including SAEs and AESIs)

##### 4.3.1.2.1 Presence

An observation will be considered an event if it has at least a verbatim term and is not a Grade 0 intensity event.

Grade 0 events should not be included in safety analysis but are included in the separate listing “Unsolicited adverse events not included in the safety analysis.”

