##### 4.3.1.2.2 Intensity

Intensity for unsolicited AEs will be derived according to the following classification: Grade 0 (None), Grade 1, Grade 2, Grade 3, or Missing

If the unsolicited AE is measurable and its preferred term is part of the list of solicited reactions, then the measurement is derived based upon and following the same rule of the intensity scales defined in the protocol for that measurable injection site or systemic reaction. Note the intensity could be considered as “None” (not a reaction) in the analysis despite being considered a reaction by the investigator (eg, swelling measurement  $> 0$  mm but  $< 25$  mm in subject aged  $\geq 12$  years).

Intensity for the other unsolicited AEs will correspond to the value reported in the eCRF.

The maximum intensity corresponds to the highest intensity for a unique term.

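### The SAP's Grade 0 exclusion for measured unsolicited events has no exemption for serious events, which conflicts with the SAP's own definition of an SAE

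*Protocol*

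**What the plan says.** **Grading.** Protocol 9.2.1.3.3 introduces its rules with "For each unsolicited AE (whether serious or non-serious), the following information is to be recorded". For measurable events that are also on the solicited list, "the size of the AE as well as the temperature for fever will be collected and analyzed based on the corresponding scale", meaning the one for solicited reactions. SAP 4.3.1.2.2 applies the same derivation, triggered as follows: "If the unsolicited AE is measurable and its preferred term is part of the list of solicited reactions". Its possible results are "Grade 0 (None), Grade 1, Grade 2, Grade 3, or Missing". It warns that the result may be no reaction at all "in the analysis despite being considered a reaction by the investigator", and gives as its example a swelling above 0 but under 25 mm at age 12 or over.

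**Exclusion.** SAP 4.3.1.2 is titled as covering SAEs and AESIs. Its first subsection, 4.3.1.2.1, requires an event to have a verbatim term and not to be Grade 0. It adds that "Grade 0 events should not be included in safety analysis" and sends them to a separate listing of unsolicited events left out of the analysis.

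**Seriousness.** SAP 4.3.1 defines an SAE as an unsolicited AE that the investigator considers serious, reconciled with the pharmacovigilance database. SAP 4.3.1.2.6 relies on the Serious tick in the eCRF. Neither mentions grade. Protocol 9.2.1.1 separates seriousness from severity. The endpoint in Protocol 9.2.1.2 is "Occurrence of SAEs and AESIs within at least 6 months after each vaccination as applicable to Cohort 1 and Cohort 2", with no size or temperature condition.

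**The concern.** The cut-offs in Protocol Tables 9.1 to 9.5 were written to grade reactogenicity. Seriousness depends on outcome or action, such as hospitalization. When a reactogenicity cut-off also decides whether an observation counts as an event, a serious event with a small measurement can fail the test, although nothing in the SAE endpoint makes the measurement relevant.

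At stake is the completeness of the SAE summaries. The injection-site case is the less comfortable one: by convention all injection-site events are treated as related (Protocol 9.2.1.3.5, SAP 5.3.2.2), so an SAE dropped this way would be a related SAE.

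**Working it through.** The plan gives no rate or count for such events, so there is no figure to reproduce. The check is a trace of the rules.

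**Step 1: cut-offs.** For erythema and swelling, Grade 1 starts above 0 mm under age 12 (Protocol Tables 9.1 and 9.2) and at 25 mm from age 12 (Table 9.3). For fever, Grade 1 starts at 38.0 °C at every age (Tables 9.4 and 9.5).

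**Step 2: apply SAP 4.3.1.2.2, then 4.3.1.2.1, to unsolicited AEs ticked Serious.**

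| Case | Derived grade | Literal result |
|---|---|---|
| Injection-site swelling or erythema, 20 mm, age 12 or over | 0 | Not an event; listing only |
| Same, 20 mm, under age 12 | 1 | Stays in the SAE table |
| Pyrexia, recorded 37.8 °C, any age | 0 | Not an event; listing only |
| Pyrexia, temperature not recorded | Missing (SAP 5.3.2.4) | Stays in the SAE table |
| Anaphylaxis, encephalitis, convulsion | As reported in the eCRF | Not affected |

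Two features stand out. The same 20 mm serious reaction is counted at age 11 and not at age 12, within one pediatric group. And a missing measurement keeps the event in, while a recorded low one takes it out.

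**Step 3: look for an exemption.** The SAP makes special provision for SAEs and AESIs in 4.3.1 (collection over the whole study) and in the unsolicited-AE part of 5.1.2.2 (onset more than 28 days after vaccination). Both concern time windows. Neither concerns Grade 0, and the analysis-set and missing-data rules (5.2.3, 5.3.2) add nothing.

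**Step 4: set the competing sections side by side.** SAP 4.3.1 says the investigator's judgement makes an SAE. SAP 4.3.1.2.6 says the tick makes an event serious, but it starts from the word event, which 4.3.1.2.1 has just defined so as to leave out Grade 0. The SAE part of 5.1.2.2 treats SAEs as a subset of the unsolicited AEs. No sentence says which section prevails.

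**Step 5: discontinuations (SAP 4.3.1.3.6).**
- Disposition table: counts the subject from the completion form, with no grade condition.
- Safety overview: counts the subject from the completion form, or from an unsolicited AE of Grade 1 or above or of missing grade. Either route is enough.
- SOC/PT table: for unsolicited AEs, only the grade-conditioned route.

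A Grade 0 event that ended participation is therefore absent from the SOC/PT table, while a subject marked as an adverse-event termination on the completion form stays in the other two.

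**Step 6: scale.** One event in a planned Cohort 1 age-specific group is 1/303 = 0.33% (VRVg-2) or 1/101 = 0.99% (each control). In Cohort 2 it is 1/414 = 0.24% or 1/138 = 0.72%. These show the weight of one event, not its likelihood.

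**The case against.** The best reply is that the SAP does not intend this result. Its SAE definitions carry no grade condition. The SAE tables in 5.1.2.2 are broken down by nature, causality, seriousness criterion and outcome, not by intensity. The protocol separates seriousness from severity. A programmer starting from the Serious tick would keep the event.

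The reach is also narrow. Only three measurable terms are involved. Under age 12 any reaction above 0 mm is at least Grade 1. Protocol 9.2.1.3.2 asks for the temperature to be taken at any apparent fever and for the highest value to be recorded, so a hospitalization for fever with a recorded value below 38.0 °C is hypothetical.

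Most of this stands. It means that removal from the SAE table is what the literal text produces, not a certainty. It does not reconcile the sections: 4.3.1.2.1 names its scope as including SAEs, exempts none, and defines the term on which 4.3.1.2.6 depends.

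Three stronger readings are tempting, and the documents do not support them:
- A reader might infer that such an SAE is lost altogether. It is not. It stays in the named listing, is reported within 24 hours (Protocol 10.1), and is reconciled with the pharmacovigilance database (Protocol 11.2, SAP 4.3.1).
- A reader might infer that it leaves every discontinuation table. Step 5 shows that the grade condition is decisive only in the SOC/PT table.
- A reader might infer that AESIs are exposed too, because the section title names them. None of the three AESIs is a measurable solicited term.

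**Conclusion.** The point holds as an unreconciled conflict within the SAP. Followed literally, 4.3.1.2.1 and 4.3.1.2.2 take a serious pyrexia below 38.0 °C, or a serious injection-site erythema or swelling below 25 mm at age 12 or over, out of the SAE summary tables. That conflicts with SAP 4.3.1 and 4.3.1.2.6 and with Protocol 9.2.1.1 and 9.2.1.2. The operative wording is in the SAP; Protocol 9.2.1.3.3 supplies only the grading scale and needs no correction.

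The importance is minor. The situation is expected to be rare, and no hypothesis, alpha or power figure depends on it. The conclusion assumes that the preferred term matches a solicited term, that a sub-threshold value was recorded, and that the exclusion is programmed as written. The finding on discontinuations further assumes that the completion form is marked for an adverse event.

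**What to change.** Add to SAP 4.3.1.2.1: *The Grade 0 exclusion does not apply to events ticked Serious or to AEs leading to study discontinuation; these are counted in the SAE and discontinuation summaries, with derived intensity shown as below Grade 1.* Make the matching edit to the unsolicited-AE condition in the SOC/PT item of 4.3.1.3.6.

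No separate AESI clause is needed. The cost is one sentence, one conforming edit and the corresponding programming condition, with no new data collection. If the sponsor already intends to keep these events, the sentence records that intention.

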9.2.1.3.4 Adverse Events of Special Interest

The following AESIs will be assessed during the overall conduct of the study:

- Anaphylactic reactions
- Encephalitis
- Convulsions

These AESIs are considered by the Sponsor to be relevant for the monitoring of the safety profile of investigational products. They will be collected during the entire participation of a subject in the study and are to be reported as SAEs according to the procedure described in [Section 10](#).

These AESIs have been defined based on existing post-marketing safety data of other rabies vaccines. For each AESI, the standard case definitions from the Brighton Collaboration will be used [\(63\)](#) [\(64\)](#) [\(65\)](#).

9.2.1.3.5 Assessment of Causality

The Investigator will assess the ***causal relationship*** between each unsolicited systemic AE and the product administered as either ***not related*** or ***related***, based on the following definitions:

Not related – The AE is clearly / most probably caused by other etiologies such as an underlying condition, therapeutic intervention, or concomitant therapy; or the delay between vaccination and the onset of the AE is incompatible with a causal relationship; or the AE started before the given vaccination

Related – There is a “reasonable possibility” that the AE was caused by the product administered, meaning that there is evidence or arguments to suggest a causal relationship

Note: By convention, all AEs reported at the injection site (whether solicited or unsolicited) and all solicited systemic AEs are considered to be related to the administered product and therefore are referred to as reactions and do not require the Investigator’s opinion on relatedness.

AEs likely to be related to the product, whether serious or not, that persist at the end of the study will be followed up by the Investigator until their complete disappearance or the stabilization of the subject’s condition. The Investigator will inform the Sponsor of the date of final disappearance of the event or the date of “chronicity” establishment.

9.2.2 Immunogenicity

9.2.2.1 Immunogenicity Endpoints

The secondary endpoints for the evaluation of immunogenicity are:

- RVNA titers (IU/mL) measured by RFFIT, summarized at the subject/ timepoint level:
- RVNA titers at D0 and D28 for subjects in Primary Series Cohort 1 and Cohort 2, and at D42 for subjects in Primary Series Cohort 1; at M12 and M12+D14 for subjects in the Booster Phase Cohort 1; at M6, M12, M18, between M24 up to M36, and between M24 up to M36+D14 for subjects in Immunogenicity Persistence and Booster Phase Cohort 2
- Subjects with an RVNA titer $\geq 0.5/\text{mL}$ at D0 and D28 for subjects in Primary Series Cohort 1 and Cohort 2, and at D42 for subjects in Primary Series Cohort 1; at M12 and M12+D14 for subjects in the Booster Phase Cohort 1; at M6, M12, M18, between M24 up to M36, and between M24 up to M36+D14 for subjects in Immunogenicity Persistence and Booster Phase Cohort 2
- Subject with an RVNA titer $\geq \text{LLOQ IU/mL}$ at D0 and D28 for subjects in Primary Series Cohort 1 and Cohort 2, and at D42 for subjects in Primary Series Cohort 1; at M12 and M12+D14 for subjects in the Booster Phase Cohort 1; at M6, M12, M18, between M24 up to M36, and between M24 up to M36+D14 for subjects in Immunogenicity Persistence and Booster Phase Cohort 2
- Individual RVNA titer ratio: D28/D0 for subjects in Primary Series Cohort 1 and Cohort 2, and D42/D0 for subjects in Primary Series Cohort 1; M12/D0, 14 days after M12/D0, and 14 days after M12/M12 for subjects in Booster Phase Cohort 1; M6/D0, M12/D0,

M18/D0, M24 up to M36/D0, 14 days after M24 up to M36/D0, and 14 days after M24 up to M36/M24 up to M36 for subjects in Immunogenicity Persistence and Booster Phase Cohort 2

- Subject with complete or incomplete neutralization at the starting dilution (1/5) of the RFFIT assay at subject with an RVNA titer \geq LLOQ IU/mL at D0 and D28 for subjects in Primary Series Cohort 1 and Cohort 2, and D42 for subjects in Primary Series Cohort 1; M12 and M12+D14 for the Booster Phase Cohort 1; at M6, M12, M18, between M24 up to M36, and between M24 up to M36+D14 for the Immunogenicity Persistence and Booster Phase Cohort 2

9.2.2.2 Immunogenicity Assessment Methods

The immunogenicity assessment methods for the secondary endpoints are the same as those presented in [Section 9.1.2.2](#).

9.2.3 Efficacy

No clinical efficacy data will be obtained in the study.

9.3 Observational Endpoints and Assessment Methods

There are no observational objectives in this study.

10 Reporting of Serious Adverse Events

To comply with current regulations on SAE reporting to health authorities, the Investigator must document all SAEs regardless of causal relationship and notify the Sponsor and the Clinical Research Associate (CRA) within the notification timelines stated in the following sections. The Investigator will give access and provide the Sponsor and the CRA with all necessary information to allow the Sponsor to conduct a detailed analysis of the safety of the investigational product(s). It is the responsibility of the Investigator to request all necessary documentation (eg, medical records, discharge summary, autopsy) in order to provide comprehensive safety information. All relevant information must then be transcribed onto the AE CRF and the appropriate Safety Complementary Information CRFs.

10.1 Initial Reporting by the Investigator

SAEs occurring during a subject's participation in the study or experiment must be reported within 24 hours to the Sponsor's GPV Department and to the CRA. Every SAE must be reported, even if the Investigator considers that it is not related to the vaccine. The Investigator (licensed physician [MD or DO]) must validate the information entered on the AE CRF by completing the Investigator validation form.

The Investigator must indicate on the AE CRF that the event was serious and must complete the relevant SAE section of this form as well as the appropriate Safety Complementary Information

CRFs. An e-mail alert will automatically be sent by the EDC system to the GPV mailbox, the CRA and the Global Clinical Development Strategy Expert (GCDSE) with relevant SAE information details.

If the EDC system is unavailable, the site must notify the Sponsor, using the paper version of the CRB, as described in the Operating Guidelines.

The Investigator must complete the paper copies of the AE CRF and of the appropriate Safety Complementary Information CRFs and send them to the Sponsor by one of the following means:

- In PDF format to the following e-mail address, using a method of transmission that includes password protection: [contact]
- [contact]

When the EDC system becomes available, the Investigator must transcribe the information from the paper forms into the EDC system.

If there is a need for urgent consultation, the Investigator is to contact the RMO. If the RMO cannot be reached, the Investigator may contact the Call Center as described in [Section 5.3](#).

10.2 Follow-up Reporting by the Investigator

The AE CRF completed initially must be updated within 24 hours after the Investigator has become aware of any new relevant information concerning the SAE (eg, outcome, precise description of medical history, results of the investigation). All relevant information must be included directly in the AE CRF and the appropriate Safety Complementary Information CRFs. An e-mail alert will be sent automatically to the GPV Department and the CRA. Copies of documents (eg, medical records, discharge summary, autopsy) may be requested by the GPV Department.

The anonymity of the subject must always be respected when forwarding this information.

10.3 Reporting of SAEs Occurring After a Subject Has Completed the Study

Any SAE that occurs after a subject has completed the study but that is likely to be related to the investigational product(s), other products (eg, a benefit vaccine), or to the experiment must also be reported as soon as possible. In such a case, the reporting procedure to be followed is identical to that described in [Section 10.1](#).

10.4 Assessment of Causality

The causal relationship between the SAE and the product administered will be evaluated by the Investigator as described in [Section 9.2.1.3.5](#).

Following this, the Sponsor's GSO will also assess the causal relationship to the product, based on the available information and current medical knowledge.

The causal relationship to study procedures will be also assessed in the CRB.

The decision to modify or discontinue the study may be made after mutual agreement between the Sponsor and the Investigator(s).

10.5 Reporting SAEs to Health Authorities and IECs / IRBs

The Sponsor will inform the relevant health authorities of any reportable SAEs according to the local regulatory requirements. Reporting to the health authorities will be according to the Sponsor's standard operating procedures.

The Sponsor's RMO will notify the Investigators in writing of the occurrence of any reportable SAEs. The Investigators will be responsible for informing the IECs or IRBs that reviewed the study protocol.

11 Data Collection and Management

